1.2.1.3. Toxicology

1.2.1.3.1. Phototoxicity

Results of a CCI showed that CCI was not cytotoxic and did not display an IC_{50} with or without ultraviolet radiation exposure, up to the highest soluble concentration tested CCI. Administration of ODV is not considered to exhibit a photosafety risk.

1.2.1.3.2. Fertility Study

A fertility and early embryonic development (FEED) study in male and female rats has been conducted. A summary of the results of this study, based on the audited draft report, is provided below.

The objectives of this FEED study were to determine the potential adverse effects/disturbances in the reproductive process resulting from CCI administration of ODV to CCI [REDACTED] rats, from premating to conception and from conception to implantation. This included identification of deficits in estrous cycling, tubal transport, implantation, development of the preimplantation stages of the embryo in the female, and functional reproductive effects (alterations in libido and epididymal sperm maturation) in the male. In addition, the toxicokinetics CCI [REDACTED] were determined from a satellite group of nonmated animals.

Four groups of male rats were administered ODV by CCI

There were no ODV-related effects on male survival, clinical and macroscopic observations, body weights, body weight gains, food consumption, and organ weights at CCI. Male reproductive performance (mating, fertility, and pregnancy indices and precoital intervals) and spermatogenic parameters were unaffected by ODV administration at CCI.

There were no ODV-related effects on female survival or clinical observations at CCI [REDACTED] or on premating and gestation body weights, body weight gains, food consumption, estrous cycle length, reproductive performance, macroscopic findings, or organ weights at CCI [REDACTED]. Intrauterine survival was also not affected by ODV administration at any dose level. All parameters in the CCI [REDACTED] were comparable to the vehicle control group.

Based on the lack of effects on reproductive performance and spermatogenic parameters, a dose level of CCI [REDACTED] was considered to be the no observed adverse effect level (NOAEL) for male reproductive toxicity of ODV when administered CCI [REDACTED] to CCI [REDACTED] rats. Based on the lack of effects on female reproductive performance, estrous cyclicity, and intrauterine survival, the NOAEL for female reproductive toxicity and embryonic toxicity was considered to be CCI [REDACTED]. These doses corresponded to mean CCI [REDACTED]

[REDACTED]

CCI [REDACTED]

1.3. Rationale for This Study

There are currently no approved oral therapeutic agents available for the treatment of COVID-19 in children < 12 years of age. All approved COVID-19 drugs for children ≥ 12 to < 18 years of age and weighing ≥ 40 kg are administered via parenteral route. The availability of an effective oral antiviral agent with a favorable benefit-risk profile would address a serious unmet medical need for the treatment of children with COVID-19.

1.4. Rationale for Dose Selection of Study Drug

The proposed dose for evaluation in Cohort 1 (participants aged ≥ 6 years to < 18 years and weighing ≥ 40 kg) is the same dose being evaluated in the adult Phase 3 Study GS-US-611-6273, which is ODV CCI [REDACTED] BID. Obeldesivir administered at single doses of 100 mg to 1600 mg and multiple doses of CCI [REDACTED] BID or 900 mg once daily for 5 days were generally safe and well tolerated in the Phase 1a study (Section 1.2.1.2.1).

[figure not shown]
A population pharmacokinetic (PopPK) model developed for ODV based on available adult PK data from the Phase 1 Study GS-US-611-6248 was revised to incorporate allometric scaling based on body weight in order to extrapolate exposures and select doses for pediatric participants ≥ 6 years of age and ≥ 20 kg. Figure 2 displays the resulting PopPK model-predicted GS-441524 concentration versus time profiles for the 5-day administration of CCI [REDACTED] BID to adults (≥ 18 years of age and weighing ≥ 40 kg), CCI [REDACTED] BID to adolescents (≥ 12 to < 18 years of age and weighing ≥ 40 kg) in the Phase 3 Study GS US 611-6549 and Study GS-US-611-6464 Cohort 1 participants (≥ 6 to < 18 years of age and weighing ≥ 40 kg), and CCI [REDACTED] BID to Study GS-US-611-6464 Cohort 2 participants (≥ 6 to < 18 years of age and weighing ≥ 20 to < 40 kg). This figure demonstrates that the predicted PK profiles for each of the pediatric weight groups are predicted to be similar to the anticipated PK profiles in adults. Figure 3 provides the boxplots of the corresponding PK parameters for adults and each of the pediatric weight groups. As the model results demonstrate, administration of CCI [REDACTED] for 5 days to pediatric

participants weighing ≥ 40 kg and CCI BID for 5 days to pediatric participants weighing ≥ 20 kg to < 40 kg results in exposures comparable to those anticipated in adult participants following CCI BID administration, and within the range of observed exposures associated with safe doses administered to adults in the Phase 1 Study GS-US-611-6248.

Therefore, the proposed doses are ODV CCI BID and CCI BID for Cohort 1 and Cohort 2, respectively (Table 2). The weight range associated with proposed dose for Cohort 2 may be confirmed prior to enrollment, based on update to the PopPK model using available additional PK data from adult Phase 1 and Phase 3 studies (including but not limited to GS-US-611-6248, GS-US-611-6273, and GS-US-611-6549).

The dose(s) for Cohorts 3 to 5 will be determined prior to enrollment using PK modeling based on data from the relative bioavailability study for the pediatric dosing formulation and any other available PK data from this pediatric study and adult studies (including but not limited to GS-US-611-6248, GS-US-611-6273, and GS-US-611-6549). Similarly, the dose(s) for Cohorts 6 and 7 will be determined using modeling based on available cumulative PK data from this pediatric study and adult studies prior to enrollment (including but not limited to GS-US-611-6248, GS-US-611-6273, and GS-US-611-6549).

[figure not shown]
Figure 2.

BID = twice daily; ODV = obeldesivir (GS-5245); PK = pharmacokinetic; y = year (age)

Adolescent refers to Study GS-US-611-6549 participants ≥ 12 years to < 18 years of age and weighing ≥ 40 kg. Cohorts 1 and 2 refer to pediatric Study GS-US-611-6464 Cohort 1 (participants ≥ 6 years to < 18 years of age and weighing ≥ 40 kg) and Cohort 2 (participants ≥ 6 years to < 18 years of age and weighing ≥ 20 kg to < 40 kg).

Figure 3.

AUC108-120 = partial area under the concentration versus time curve from time 108 hours to time 120 hours (the evening dose on Day 5); BID = twice daily; C_{\max} = maximum observed concentration of drug; C_{trough} = concentration at the end of the dosing interval; ODV = obeldesivir (GS-5245); PK = pharmacokinetic; y = year (age)

Adolescent refers to Study GS-US-611-6549 participants ≥ 12 years to < 18 years of age and weighing ≥ 40 kg. Cohorts 1 and 2 refer to pediatric Study GS-US-611-6464 Cohort 1 (participants ≥ 6 years to < 18 years of age and weighing ≥ 40 kg) and Cohort 2 (participants ≥ 6 years to < 18 years of age and weighing ≥ 20 kg to < 40 kg).

1.5. Benefit-Risk Assessment for the Study

Obeldesivir has shown to have activity in animal models and shares the same active triphosphate metabolite as the approved COVID-19 treatment drug, RDV.

Obeldesivir has also been evaluated in a Phase 1 (single and ascending dose) study where it was safe and well tolerated. Obeldesivir is currently being evaluated in 2 Phase 3 adult population studies (GS-US-611-6273 and GS-US-611-6549). Enrollment in this study will be initiated following the review of safety data from the first occurring Data Monitoring Committee (DMC) of the adult program:

- Data from the first 200 participants, who completed Day 29 visit or prematurely discontinued from the study, in GS-US-611-6273 have been reviewed by the DMC

OR

- Data from the first 150 participants, who completed Day 29 visit or prematurely discontinued from the study, in GS-US-611-6549 have been reviewed by the DMC.

Obeldesivir has the potential benefit to be the first oral COVID treatment for children, which will facilitate treatment of outpatients as well as inpatients.

Potential risks of a participant's study involvement include unknown AEs, general risks associated with laboratory blood draws, and the associated pain and discomfort of phlebotomy.

Strategies to mitigate these risks include close monitoring of participants' clinical statuses, laboratory values, and AEs. Parameters for discontinuation of the study drug due to AEs will be clearly defined and closely followed.

An infectious disease pandemic may pose additional risks to study drug availability, the study visit schedule, and adherence to protocol-specified safety monitoring or laboratory assessments. Refer to Appendix [11.3](#) for further details on the risks and risk mitigation strategy.

Considering the above, the benefit-risk balance for this study is considered positive.

2. OBJECTIVES AND ENDPOINTS

Primary Objectives	Primary Endpoints

• To evaluate the plasma PK of ODV in pediatric participants with COVID-19• To evaluate the safety and tolerability of ODV in pediatric participants with COVID-19	
• PK parameters (AUC₀₋₁₂, C_{max}, and C_{trough}) for ODV metabolite, GS-441524• Incidence of treatment-emergent AEs by Day 35• Incidence of treatment-emergent laboratory abnormalities by Day 35
Secondary Objectives	Secondary Endpoints

• To assess the impact of ODV on time to sustained alleviation of targeted COVID-19 symptoms in pediatric participants with COVID-19• To evaluate the antiviral activity of ODV on SARS-CoV-2 nasal swab viral load in pediatric participants with COVID-19• To assess the impact of ODV on the requirement for supplemental oxygen in pediatric participants with COVID-19• To evaluate palatability and acceptability of ODV in pediatric participants with COVID-19• To provide data on the use of medications other than RDV and ODV for treatment of COVID-19 in pediatric participants with COVID-19• To assess the impact of ODV on COVID-19-related hospitalizations or all-cause death in pediatric participants with COVID-19	
• Time to sustained alleviation of targeted COVID-19 symptoms by Day 35• Change from baseline in SARS-CoV-2 nasal swab viral load at Day 5• Proportion of participants who require supplemental oxygen support (low flow oxygen, high flow oxygen, noninvasive ventilation, mechanical ventilation, or extracorporeal membrane oxygenation) by Day 35• Assessment of palatability and acceptability scores of each formulation at Day 5• Proportion of participants with concomitant use of medications other than RDV and ODV for treatment of COVID-19 by Day 35• Proportion of participants with COVID-19-related hospitalization or all-cause death by Day 35

CCI

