3. STUDY DESIGN

3.1. Study Design Overview

This will be a single-arm, open-label study to evaluate the safety, PK, and efficacy of ODV in pediatric participants with COVID-19 who are at risk of progression to severe disease.

After screening procedures, eligible participants will receive treatment with ODV.

At least 52 participants aged 0 days to < 18 years will be enrolled as described in [Table 2](#). Participants will be enrolled in a staggered manner. Cohorts will be opened for enrollment based upon availability of a suitable pediatric formulation and availability of preliminary safety and PK data.

[Figure 1](#) provides an overview of study design.

Table 2. Study Cohort Description

Cohort	Description
Pediatric participants ≥ 28 days to < 18 years old	
1	≥ 6 years to < 18 years and weight ≥ 40 kg
2	≥ 6 years to < 18 years and weight ≥ 20 kg to < 40 kg
3	≥ 2 years to < 18 years and weight ≥ 12 kg to < 20 kg
4	≥ 28 days to < 18 years and weight ≥ 3 kg to < 12 kg
Term neonatal participants 0 days to < 28 days old	
5	≥ 14 days to < 28 days of age, GA ≥ 37 weeks and weight ≥ 2.5 kg
6	0 days to < 14 days of age, GA ≥ 37 weeks and birth weight ≥ 2.5 kg
Preterm neonates and infants 0 days to < 56 days old	
7	0 days to < 56 days of age, GA < 37 weeks and birth weight ≥ 1.5 kg

GA = gestational age

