5.3. Prior and Concomitant Medications

5.3.1. Prior and Concomitant Medications That Are Prohibited or Used With Caution

Medications in [Table 4](#) are prohibited or to be used with caution while participants are taking study drugs. In instances where a prohibited medication is initiated before discussion with the Gilead medical monitor, the investigator must notify Gilead as soon as he/she is aware of the use of the prohibited medication.

There are no restrictions on the symptomatic treatment of COVID-19 other than those indicated in [Table 4](#). There are no restrictions on concomitant medications based on potential for PK DDI with ODV.

Table 4. Prior and Concomitant Medications That Are to Be Used With Caution or That Are Prohibited Because of Impact on Efficacy Assessments or Participant Safety

Medication Class	Medications to Be Used With Caution	Prohibited Medications ^a
COVID-19 medications	—	RDV, molnupiravir, nirmatrelvir/ritonavir, monoclonal antibodies against COVID-19

COVID-19 = coronavirus disease 2019; RDV = remdesivir

a Concomitantly with ODV.

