8.6.4. Other Safety Evaluations

The proportion of participants with concomitant use of medications other than RDV and ODV for treatment of COVID-19 will be provided in summary tables by cohort and overall.

Palatability and acceptability will be summarized using descriptive statistics by cohort and overall.

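### The count of other COVID-19 medications leaves out remdesivir, which is not a study drug here, so a participant treated only with remdesivir by Day 35 appears in no visible endpoint

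*Protocol*

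**What the plan says.** The objective in Section 2 of the protocol is "To provide data on the use of medications other than RDV and ODV for treatment of COVID-19 in pediatric participants with COVID-19". The endpoint beside it is the "Proportion of participants with concomitant use of medications other than RDV and ODV for treatment of COVID-19 by Day 35". Section 8.6.4 carries the same exclusion into the analysis, both for each cohort and for all participants together: "The proportion of participants with concomitant use of medications other than RDV and ODV for treatment of COVID-19 will be provided in summary tables". The synopsis repeats the exclusion in its objectives table and in its statistical methods.

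ODV is the only study treatment. Section 3.1 states: "After screening procedures, eligible participants will receive treatment with ODV".

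Table 4 in Section 5.3.1 has one row of prohibited COVID-19 medications: "RDV, molnupiravir, nirmatrelvir/ritonavir, monoclonal antibodies against COVID-19". Its footnote limits the prohibition to use "Concomitantly with ODV", and the text above the table says the same. Section 3.2 sets dosing at 5 days. Exclusion criterion 1 in Section 4.3 names intravenous RDV among the therapies whose anticipated use rules a child out, but only for use less than 5 days after screening. Section 1.1 describes RDV as approved for hospitalized and nonhospitalized patients, pediatric and adult.

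**The concern.** A count of other treatments naturally leaves out the study drug. Leaving out RDV as well would make sense in a trial where RDV was also a study treatment, but here it is not. In Table 4 and in exclusion criterion 1 the protocol places RDV in the same class as molnupiravir, nirmatrelvir/ritonavir and monoclonal antibodies. The endpoint then counts those three and drops RDV, and gives no reason.

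What is at stake is how the figure can be read. A reader of the study report will probably take it as the share of children who received further COVID-19 treatment. If some received RDV and nothing else, the figure is too low. The error can only go in that direction.

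**Working it through.** The plan gives no figure for this endpoint, so there is none to reproduce. Its only computed figure, the power for PK equivalence, plays no part here.

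**Step 1: is there a period in which RDV is allowed but not counted?**

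| Item | Source | Period |
|---|---|---|
| Table 4 prohibition of RDV | Section 5.3.1 | While ODV is taken, about Days 1 to 5 |
| Exclusion for anticipated COVID-19 therapy | Section 4.3, criterion 1 | Less than 5 days after screening |
| Endpoint window | Section 2 | To Day 35 |
| Safety data summarized | Section 8.6 | To last dose plus 30 days |

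Days 6 to 35 lie inside the endpoint window and outside the Table 4 prohibition: 35 − 5 = 30 of 35 days. The word concomitant in the endpoint cannot mean only during ODV dosing, or a window to Day 35 would serve no purpose.

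**Step 2: is RDV use counted elsewhere?** The other secondary endpoints concern symptoms, viral load, supplemental oxygen, palatability, and hospitalization or death. None counts RDV users. In Section 8.5.2, rescue medication taken before alleviation censors the symptom endpoint at Day 34, but the rescue drugs are not listed and no count of users follows from this. Text after the endpoint table in Section 2 is redacted, so the check covers visible endpoints only.

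**Step 3: size.** Let n be the participants in the denominator, m those who used a COVID-19 drug other than RDV or ODV, and k those who used RDV and no other such drug.

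- As written: m/n
- With RDV counted: (m + k)/n
- Shortfall: (m + k)/n − m/n = k/n, whatever m is

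The denominators come from Sections 4.1 and 8.9: 12 evaluable participants in each of Cohorts 1 to 4, and at least 52 overall. The documents give no value for k, so the values below are assumptions.

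| k | n | Shortfall k/n |
|---|---|---|
| 1 | 12 | 8.3 points |
| 2 | 12 | 16.7 points |
| 3 | 12 | 25.0 points |
| 1 | 52 | 1.9 points |
| 3 | 52 | 5.8 points |
| 5 | 52 | 9.6 points |

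If nobody used another COVID-19 drug (m = 0) and k = 5, the report would show 0/52 = 0% (exact 95% CI 0 to 6.8%), against 5/52 = 9.6% (3.2 to 21.0%) with RDV counted. The values 0% and 9.6% need the assumption m = 0; the shortfall of 9.6 points does not.

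**Step 4: the link to PK.** GS-441524 is the PK analyte (Section 2) and is described as the parent nucleoside of RDV (Sections 1.1 and 1.2.1.1). PK samples in Cohorts 1 and 2 are taken on Days 3 and 5, and the PK Analysis Set (Section 8.3.1.3) does not leave out participants who took RDV. RDV given during dosing, although prohibited, could therefore affect the primary PK data. RDV given after dosing could not affect those samples.

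**The case against.** The strongest reply is that nothing is misstated. Objective, endpoint and analysis use the same definition, and the endpoint measures what its objective asks. The label tells every reader that RDV is left out. There may also be a reason for it: RDV and ODV share an active metabolite (Section 1.5), so setting the pair apart from other COVID-19 drugs is a coherent grouping. Use during dosing must be notified to the sponsor under Section 5.3.1. Clinical worsening is covered by the oxygen and hospitalization endpoints. The analysis is descriptive, with no comparator and no test.

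Most of this stands, and it limits the point. It does not remove it. The protocol does not give the shared metabolite as its reason, and the grouping still leaves RDV use untabulated. Notification covers only the dosing period. The oxygen and hospitalization endpoints do not show who received RDV. The SAP could add an RDV table, but it could not count RDV toward this endpoint without departing from the protocol's definition.

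Three stronger readings are tempting, and the documents do not support them:

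- **RDV users are reported as having had no additional treatment.** The label discloses the exclusion, and no section says the remaining participants received nothing. They are simply not counted, and only if they took no other COVID-19 medication.
- **RDV is the likely rescue drug.** The protocol names no rescue drug and gives no expected frequency of RDV use.
- **The endpoint makes ODV look more effective.** The plan draws no efficacy inference from this measure.

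**Conclusion.** The point holds in a limited form. The protocol fixes a numerator that leaves out an approved, non-study COVID-19 drug, and no visible endpoint picks up its use. The proportion can understate additional COVID-19 treatment by k/n, where k is the number of participants treated only with RDV: 8.3 points per participant in a cohort of 12 and 1.9 points in 52. A larger denominator makes each step smaller. Because k is unknown, these figures show sensitivity and not an expected bias. If no participant receives RDV alone, the shortfall is zero.

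The sections do not contradict one another. The effect is confined to one descriptive secondary endpoint; the primary endpoints as defined and the sample size are unaffected. Severity is low, and the change is a free improvement.

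**What to change.** In the synopsis, Section 2 and Section 8.6.4, define the measure as the proportion of participants using COVID-19 medications other than ODV by Day 35, and align the objective with it. State the Day 35 limit in Section 8.6.4 as well. Show RDV on its own line, split by start and stop dates into use during ODV dosing and use after the last ODV dose. The line for use during dosing also identifies participants whose GS-441524 concentrations need care in the PK analysis.

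If the sponsor wants to keep RDV and ODV together as a pair, the present figure can stay as a sub-row with the reason stated, provided the RDV count is shown beside it.

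The cost is wording in three places and a few table rows. Concomitant medications are already collected (Table 1 and Section 6.3.2.3), and Section 9.1.5 requires their start and end dates in the source data. Enrollment, sample size and the rules on permitted treatment do not change.

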3. STUDY DESIGN

3.1. Study Design Overview

This will be a single-arm, open-label study to evaluate the safety, PK, and efficacy of ODV in pediatric participants with COVID-19 who are at risk of progression to severe disease.

After screening procedures, eligible participants will receive treatment with ODV.

At least 52 participants aged 0 days to < 18 years will be enrolled as described in [Table 2](#). Participants will be enrolled in a staggered manner. Cohorts will be opened for enrollment based upon availability of a suitable pediatric formulation and availability of preliminary safety and PK data.

[Figure 1](#) provides an overview of study design.

Table 2. Study Cohort Description

Cohort	Description
Pediatric participants ≥ 28 days to < 18 years old	
1	≥ 6 years to < 18 years and weight ≥ 40 kg
2	≥ 6 years to < 18 years and weight ≥ 20 kg to < 40 kg
3	≥ 2 years to < 18 years and weight ≥ 12 kg to < 20 kg
4	≥ 28 days to < 18 years and weight ≥ 3 kg to < 12 kg
Term neonatal participants 0 days to < 28 days old	
5	≥ 14 days to < 28 days of age, GA ≥ 37 weeks and weight ≥ 2.5 kg
6	0 days to < 14 days of age, GA ≥ 37 weeks and birth weight ≥ 2.5 kg
Preterm neonates and infants 0 days to < 56 days old	
7	0 days to < 56 days of age, GA < 37 weeks and birth weight ≥ 1.5 kg

GA = gestational age

3.2. Duration of Intervention

Duration of dosing is 5 days.

3.2.1. Poststudy Care

The long-term care of the participant will remain the responsibility of his/her primary treating physician.

3.3. Protocol-Specific Discontinuation Criteria

3.3.1. Criteria for Early Discontinuation for the Individual Participants

3.3.1.1. Criteria for Early Discontinuation for the Individual Participants From Study Intervention

Study drug will be discontinued in the following instances:

- Any SAE suspected to be related to study drug.
- Any \geq Grade 3 AE suspected to be related to study drug.
- An AE, or worsening of clinical condition requiring clinical intervention, that would, in the judgment of the investigator, affect assessments of clinical status to a significant degree.
- Any \geq Grade 3 clinically significant laboratory abnormality (if confirmed by repeat testing) suspected to be related to study drug.
- eGFR < 50 mL/min/1.73 m² (≥ 1 year of age) using the Bedside Schwartz formula.
- Alanine aminotransferase (ALT) $\geq 5 \times$ upper limit of normal (ULN).
- Bilirubin $\geq 2 \times$ ULN ($\geq 3 \times$ ULN for participants with Gilbert's syndrome).
- Unacceptable toxicity, as defined in Section [7.7](#), or toxicity that, in the judgment of the investigator, compromises the ability to continue study-specific procedures or is considered not to be in the participant's best interest.
- Participant request to discontinue for any reason.
- Participant noncompliance with the study protocol.
- Pregnancy (refer to Appendix [11.4](#)).
- Discontinuation of the study by sponsor.
- Creatinine level above the thresholds described in [Table 3](#) if < 1 year of age.

Table 3. Creatinine Value Cutoff by Age Group

Gestational age	Chronological age	Creatinine Value Cutoff in mg/dL
≥ 24 to ≤ 27 weeks	0 to < 28 days	CC1
≥ 28 to ≤ 29 weeks	0 to < 14 days	CC1
≥ 30 to < 32 weeks	0 to < 7 days	CC1
	≥ 7 days to 1 month	CC1
	≥ 1 to < 2 months	CC1
	≥ 2 months to < 1 year	CC1
≥ 32 weeks	0 to < 2 days	CC1
	≥ 2 to < 7 days	CC1
	≥ 7 days to 2 months	CC1
	≥ 2 months to < 1 year	CC1

* Creatinine values CC1

